Procedures: N=40 parent/child dyads will receive a weekly monetary incentive for losing weight during an initial 12 week weight-loss program. During this time, half of the families will receive EFT training (N=20) and the other half will receive a control thought training program (N=20). After 12 weeks, the monetary incentives program will be terminated, but the parent/child dyads will continue their respective EFT or control thought training programs for an additional 12 weeks. At the end of the additional 12 weeks, weight-loss maintenance will be examined between dyads that received EFT and dyads that received control thought training.

Procedures Cohort 2:

Procedures: N=20 parent/child dyads will receive a weekly monetary incentive for losing weight during an initial 8 week weight-loss program. During this time, half of the families will receive EFT training (N=10) and the other half will receive a control thought training program (N=10). After 8 weeks, the monetary incentives program will be terminated, but the parent/child dyads will continue their respective EFT or control thought training programs for an additional 8 weeks. There will then be an 8 week no intervention follow-up period. At the end of the follow-up period, weight-loss maintenance will be examined between dyads that received EFT and dyads that received control thought training.

Purpose (Cohort 3): To assess whether episodic future thinking (EFT), thought training that teaches individuals to think prospectively about future events as if they were happening now, promotes healthier grocery shopping behaviors in parent and child dyads in which the child is obese/overweight, and to assess subsequent weight loss.

Procedures Cohort 3:

N=6-12 parent/child dyads will receive the full family-based therapy program with a specialized EFT component focused on grocery shopping during this 15 week weight-loss program. This study is a nonconcurrent multiple baseline design; participants will be randomized to a 4 week, 7 week, or 10 week group with staggered baseline periods followed by 4-8 weeks of the intervention consisting of FBT and EFT.

1.4 Specify your research question(s), study aims or hypotheses: We hypothesize that:

1) Parent/child dyads in both the EFT and the CONTROL thought training conditions will lose weight with the monetary incentive program.

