Session 1- In-Lab Screening- After a brief overview of the study and signing the consent documents, objective measures of height and weight will be collected to ensure participants meet the BMI eligibility criteria. The parent and child will then undergo the remainder of the screening session visit in separate rooms. Participants may also complete: 1) disordered eating behavior via the Eating Disorders Examination Questionnaire (EDE) for parents & Kid's Eating Disorders Survey (KEDS) for kids, 2) a sociodemographic questionnaire, 3) a clinical interview to ensure they do not meet any of the exclusion criteria, 4)The Patient Health Questionnaire (PHQ) to assess depressive symptoms, and 5)K-SADS. Children will not be asked question number 9 on the PHQ which asks, "over the past 2 weeks, how often have you been bothered by any of the following problems...thoughts that you would be better off dead, or of hurting yourself." Additionally, if the Patient Health Questionnaire is not completed during the visit, it may be completed over the phone. If a participant's score on any of the questionnaires is out of the normal range, a follow-up visit or phone call may be required. During the follow-up, a trained research team member will administer the K-SADS, or a supplement of the K-SADS, to further assess questionnaire results. The follow-up may also be conducted to probe ambiguous participant responses on the eating disorder questionnaires. This will allow research team members to follow-up on any concerns with participant psychopathology. If participants are still eligible after the in-lab screening, they will be randomized to either the EFT or CONTROL thought training group and a baseline visit will be scheduled.

If any potential participants are ineligible because they show signs of baseline disordered eating patterns or major psychopathology/distress, research assistants will report it to the study contact person and PI of the study, [name], who will help the families find the appropriate resources for help. Participants who are ineligible for other reasons (e.g. do not meet the BMI overweight/obesity criterion) will be given basic information about healthy living to use as a personal resource.

Randomization: After eligible participants complete the in-lab screening session, parent/child dyads will be randomized to receive either EFT training or the CONTROL thought training program and a baseline session will be scheduled.

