 - Procedures include a confederate pretending to be another participant in the study.
 - Participants will be told that the research includes completion of a particular task, when in fact, that task will not be administered.
 - Study is designed to introduce a new procedure (or task) that participants are not initially told about.

No

- **1.18** Indicate any payments or reimbursements to participants (check all that apply)
 - CashGift or Debit Card
- 1.19 Does this study have a plan to have an individual or committee review combined data from all participants on a periodic basis (such as summary or aggregate safety and/or efficacy data)? No
- **1.20** What have you done to minimize any risks?
 - No foreseeable risks
 - Psychological consultation and/or referrals readily available
 - **1.21** What are the potential benefits related to this project for:
 - the participant (if any)
 - benefits to society (if any)

There are many potential benefits of the proposed research. Participants in the study could gain new knowledge on how episodic future thinking influences inter-temporal decision making. All participants in all groups are taught methods for healthier grocery shopping, eating and living; therefore, depending on the behavior changes of the participants, it could result in a healthier eating behaviors and a healthier home environment. This in turn could result in potential weight loss for the entire family in the home. If participants do lose weight in the study, it could decrease their risk of weight-related disease such as type 2 diabetes and heart disease.

1.22 Provide a summary of the analysis methods you will use, including, if applicable, the data points or outcomes you will analyze.

Cohort 1:

Preliminary analyses:

Preliminary analyses will be conducted to ensure groups are similar based on demographic characteristics (age, BMI, race/ethnicity, SES).

Primary analyses:

Between group ANOVAs will be performed to make sure the two groups have similar continuous characteristics (age, BMI for adults/percent over BMI for children) and chi-square analyses will be performed to ensure the groups have similar categorical characteristics (race/ethnicity, SES). If a group difference is found, the variable will be entered as a covariate in subsequent analyses.

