Two-way repeated measures ANOVAs will then be conducted to determine differences in BMI/percent over BMI, weight, and waist circumference, between the EFT and HT groups over time. Data points will be collected at weeks 2 (baseline), 7, 10, 14 (incentive program ends), 18, and 26 of the program. We hypothesize:

1- The EFT and HT group will both have a reduction in BMI/percent over BMI, weight, and waist circumference from baseline throughout the monetary incentives program (week 7, 10, 14).

2- The EFT group will have a greater reduction in BMI/percent over BMI, weight, and waist circumference from baseline throughout the monetary incentives program (week 7, 10, 14) than the HT group.

3- The EFT group will maintain the reduction in BMI/percent over BMI, weight, and waist circumference from baseline after the termination of the monetary incentives program (week 18, 26).

4- The HT group will not maintain the reduction in BMI/percent over BMI, weight, and waist circumference from baseline after the termination of the monetary incentives program (week 18, 26).

Secondary analyses:

A two-way repeated measures ANOVA will be conducted to determine differences in delay discounting between the EFT and HT groups over time. Data points will be collected at weeks 2 (baseline), 7, 10, 14 (incentive program ends), 18, and 26 of the program. We hypothesize:

- 1- The EFT group will have a reduction in delay discounting over time (7, 10, 14, 18, 26) compared to baseline.
- 2- The HT group will not have a reduction in delay discounting over time (7, 10, 14, 18, 26) compared to baseline.

3- The EFT vs. the HT group will have a reduction in delay discounting over time (7, 10, 14, 18, 26).

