Regression analyses will also be conducted to determine whether baseline characteristics predict outcome variables (BMI for adults/percent over BMI for children, weight, waist circumference, and DD). These characteristics will be collected from baseline surveys including the Consideration of Future Consequences Scale, Living to 75 Assessment, and Palatable Eating Motives Scale. First, zero order correlations between each predictor and the outcome variables will be established, and then significant predictors will be entered in a multiple regression model that includes demographic characteristics and the significant predictors. This will provide the opportunity to assess what individual characteristics predict child and adult success. In addition, we will assess the influence of parental success on child success in a multiple regression model, again controlling for demographic characteristics.

Cohort 2:

Preliminary analyses will be conducted to ensure groups are similar based on demographic characteristics (age, BMI, race/ethnicity, SES).

Primary analyses: Between group ANOVAs will be performed to make sure the two groups have similar continuous characteristics (age, BMI for adults/percent over BMI for children) and chi-square analyses will be performed to ensure the groups have similar categorical characteristics (race/ethnicity, SES). If a group difference is found, the variable will be entered as a covariate in subsequent analyses.

Two-way repeated measures ANOVAs will then be conducted to determine differences in BMI/percent over BMI and weight between the EFT and HT groups over time. Data points will be collected at sessions 3 (baseline), 11 (monetary incentives end), 19, 20. We hypothesize:

1- The EFT and HT group will both have a reduction in BMI/percent over BMI and weight, and waist circumference from baseline throughout the monetary incentives program (session 11).

2- The EFT group will have a greater reduction in BMI/percent over BMI and weight throughout the monetary incentives program (session 11) than the HT group.

3- The EFT group will maintain the reduction in BMI/percent over BMI and weight from baseline after the termination of the monetary incentives program (session 19, 20).

4- The HT group will not maintain the reduction in BMI/percent over BMI and weight from baseline after the termination of the monetary incentives program (session 19, 20).

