Secondary analyses: A two-way repeated measures ANOVA will be conducted to determine differences in delay discounting between the EFT and HT groups over time. Data points will be collected at sessions 2 (baseline), 11 (incentive program ends), 19, and 20. We hypothesize:

1- The EFT group will have a reduction in delay discounting over time (11, 19, 20) compared to baseline.

2- The HT group will not have a reduction in delay discounting over time (11, 19, 20) compared to baseline.

3- The EFT vs. the HT group will have a reduction in delay discounting over time (11, 19, 20).

Regression analyses will also be conducted to determine whether baseline characteristics predict outcome variables (BMI for adults/percent over BMI for children, weight, and DD). These characteristics will be collected from baseline surveys including the Consideration of Future Consequences Scale, Living to 75 Assessment, and Palatable Eating Motives Scale. First, zero order correlations between each predictor and the outcome variables will be established, and then significant predictors will be entered in a multiple regression model that includes demographic characteristics predict child and adult success. In addition, we will assess the influence of parental success on child success in a multiple regression model, again controlling for demographic characteristics.

The results of this study will be analyzed graphically as well as assessing the degree of change from baseline to treatment across the three replications.

1.23 Provide the rationale or power analysis to support the number of participants proposed to complete this study. This is the first study of this kind, therefore, we were unable to conduct a power analysis. Additionally, a power analysis is not applicable to this multiple baseline design. We are collecting weekly data from participants and will have enough data points to ensure we will be able to achieve the study objectives. The results of this study will be analyzed graphically as well as assessing the degree of change from baseline to treatment across the three replications. For an example of a study that utilized a multiple baseline design, see:

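### The regression of child success on parental success leaves out study arm, which parent and child share, so a treatment effect can pass for parental influence

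*Combined protocol and SAP*

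**What the plan says.** The analysis is the last of the secondary analyses in section 1.22 for Cohort 1, and the sentence recurs for Cohort 2: "we will assess the influence of parental success on child success in a multiple regression model, again controlling for demographic characteristics".

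The word 'again' points back to the preceding regression on baseline survey scores. For Cohort 1, that text says "significant predictors will be entered in a multiple regression model that includes demographic characteristics and the significant predictors". No arm term appears there either.

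The preliminary analyses in section 1.22 show what counts as demographic: the check is that "groups are similar based on demographic characteristics (age, BMI, race/ethnicity, SES"). Arm is not on that list. The one general covariate rule in section 1.22 adds baseline variables on which the groups turn out to differ, so it cannot bring arm in.

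On the unit of randomisation, section 1.13 (Cohort 1, Randomization) says "parent/child dyads will be randomized to receive either EFT training or the CONTROL thought training program". Section 1.3 allocates families, half to each arm, in both cohorts: 20 and 20 in Cohort 1, 10 and 10 in Cohort 2.

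On the expected effect, hypothesis 2 of the Cohort 1 primary analyses reads "The EFT group will have a greater reduction in BMI/percent over BMI, weight, and waist circumference from baseline", compared with the control group. BMI is the adult measure and percent over BMI the child measure. Hypothesis 2 in section 1.4 states the maintenance benefit for parent/child dyads as such.

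**The concern.** Arm is fixed by randomisation before either outcome exists, is identical for both members of a dyad, and is expected to move both outcomes the same way. That makes it a confounder of the relation between parent outcome and child outcome. It is not a mediator, and conditioning on it removes no genuine parental effect: if a parent's success does help the child, that shows within each arm.

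With arm omitted, the parent coefficient mixes two things: the association between parent and child within an arm, and the fact that EFT dyads sit higher on both outcomes than control dyads. The plan intends to describe the result as influence. The chance of wrongly claiming it rises with the treatment effect the trial hopes to find, so the claim is least reliable when the intervention works best. The confounder is also known without error for every dyad.

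**Working it through.** **Plan's own figure.** There is none. Section 1.23 says no power analysis could be done, and no effect size, SD or alpha is given for this regression. The effect sizes and the two-sided 5% level below are assumptions.

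**Inputs from the documents.** 40 dyads split 20:20 (Cohort 1) and 20 dyads split 10:10 (Cohort 2), from section 1.3; randomisation by dyad, from sections 1.3 and 1.13; demographic covariates only, from section 1.22.

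**Assumptions.** Within-arm SD of 1 for each member; the same standardised arm effect d in parent and child; no parent-child association within an arm.

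**Formula.** Code arm A as −½ or +½, so Var(A) = 1/4. Let P = dA + e₁ for the parent and C = dA + e₂ for the child, with e₁ and e₂ independent. Then

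- Cov(P, C) = d²/4
- Var(P) = Var(C) = 1 + d²/4
- slope of C on P without arm (equal here to the correlation) = (d²/4) / (1 + d²/4)

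With the numbers put in:

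- d = 0.5: 0.0625 / 1.0625 = 0.059
- d = 0.8: 0.16 / 1.16 = 0.138
- d = 1.0: 0.25 / 1.25 = 0.200
- d = 1.5: 0.5625 / 1.5625 = 0.360

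The true slope is 0 in every case.

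**False-positive rate by simulation.** Child outcome was regressed on parent outcome by ordinary least squares, with a two-sided t test at 5%. One set of runs (10,000 per cell) had no demographic covariates. Another (6,000 per cell) had four normal covariates standing in for the demographics.

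| d | 40 dyads, arm omitted, no covariates | 40 dyads, arm omitted, 4 covariates | 40 dyads, arm included, no covariates | 20 dyads, arm omitted, no covariates | 20 dyads, arm omitted, 4 covariates | 20 dyads, arm included, no covariates |
|---|---|---|---|---|---|---|
| 0 | 5.3% | – | 5.1% | 5.0% | – | 4.7% |
| 0.5 | 6.5% | 6% | 5.0% | 5.8% | 5% | 5.2% |
| 0.8 | 13.9% | 13% | 4.9% | 8.5% | 9% | 4.7% |
| 1.0 | 24.1% | 22% | 4.9% | 13.7% | 12% | 5.2% |
| 1.5 | 67.4% | – | 4.8% | 37.2% | – | 4.7% |

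With the four covariates and arm included, the rate was also about 5%. The simulated mean slopes agree with the formula when arm is omitted (for example 0.142 at d = 0.8 and 0.205 at d = 1.0, 40 dyads) and are about 0 when it is included.

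**Unequal effects.** With d = 1.0 in parents and 0.5 in children, the slope is (1.0 × 0.5 / 4) / (1 + 1.0²/4) = 0.125 / 1.25 = 0.10. The simulated false-positive rate with 40 dyads is 9.4%.

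**The case against.** **Silence is not exclusion.** Section 1.22 asks only for a summary, this model gets one sentence, and an analyst might add arm unprompted. That is possible. But the sentence does name its covariates, as does the Cohort 1 model it refers back to, and arm is in neither. If arm was intended, writing it down costs nothing.

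**The bias is conditional and may be small.** It needs an arm effect in both members. With none there is no bias, and at d = 0.5 the error rate is close to nominal in both cohorts. The control arm is active: its members also generate and retrieve cues, and the incentives, teaching and case management are described without distinction by arm. Both arms are expected to lose weight. Nothing in the documents supports a large d. All of this stands and limits the size of the problem. It does not make the omission sound, because the plan itself predicts an arm difference.

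**Arm is only one shared cause.** Parent and child share a household and case management, and earn a bonus when both meet their goals (section 1.13, both cohorts). Suppose a non-causal within-arm correlation of 0.3. With 40 dyads and arm in the model, the slope stays at 0.30 and is significant in about 42–43% of runs. Omitting arm at d = 0.5 moves the slope only to (0.3 + 0.0625) / 1.0625 = 0.34. This also stands: adjusting for arm does not make the coefficient causal, and the 5% rate after adjustment holds only if no other shared cause operates. It is the reason the wording should change along with the model.

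**Low consequence.** This is a secondary analysis with no numbered hypothesis, and success is not defined for it. True, but exploratory status does not excuse leaving out a known, fully observed confounder.

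**Conclusion.** The concern holds. As written, the regression in both cohorts omits a variable that is common to the two members of every dyad and is expected to affect both outcomes. If EFT works in parents and children alike, the parent coefficient is biased upwards. The bias is slight at d = 0.5 (spurious slope 0.06) and material from about d = 0.8 (0.14, with 13% false positives in Cohort 1 and 9% in Cohort 2). At d = 1.0 it reaches 0.20, with 22% and 12%. These figures rest on assumed effect sizes, equal effects in both members, and no other source of parent-child association. The omission itself is certain from the text; its size is not known in advance. It should be corrected, but it touches one secondary analysis and leaves the randomised comparison of EFT with control as it is.

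**What to change.** In section 1.22, for both Cohort 1 and Cohort 2, name study arm as a covariate alongside the demographic characteristics in the regression of child success on parental success. If the two cohorts are ever pooled for this analysis, add cohort as well. Describe the parent coefficient as a within-arm association, not as influence, and note that the shared household and the joint bonus remain as possible explanations. Any version without arm should be labelled descriptive. A term for parental success by arm could be considered as an exploratory addition.

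The cost is one covariate, one degree of freedom and a sentence or two in section 1.22. No new data are needed.

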Experimental Group- Episodic Future Thinking (EFT) Group with Staggered Baselines (4 week, 7 week, 10 week) Unlike Cohort 1 and 2, there will be no CONTROL (HT) group – all families will receive EFT, however the time at which it is

introduced will differ between groups.

Both groups will include parent/child dyads, with the child with overweight or obesity Inclusion:

1- Child age between 10 -14

2- Child height and weight that calculates to a BMI above the 85th percentile (BMI in overweight/obesity range – normal is okay, as parent BMI is no longer a primary outcome)

3- Parent height and weight that calculates to a BMI above 18 (Cannot be within the underweight category)

- 4- Possession of at least one electronic device (per family) with WiFi capabilities (e.g. smartphone, tablet, computer)
- 5- Home internet access
- 6- Motivation to learn healthy behaviors

Exclusion:

1- Disordered eating patterns (e.g. binge-eating disorder, extreme weight-loss behaviors)

- 2- A family history of eating disorders (siblings, children, parents, or grandparents)
- 3- Medical conditions that are known to interfere with weight-loss (e.g. type 1 diabetes, thyroid disease)

4- Medical conditions that may affect their ability to use the computer for a prolonged period of time or follow study protocol

5- Psychopathology or disabilities that would limit adherence to protocol (e.g. depression, suicidality, ADHD). Participant will only be excluded if the disability would not allow them to adhere to protocol. Just having the disability does not exclude them. Suicidality would be automatically be exclusionary)

- 6- Substance use, abusé, or dependence (e.g. binge drinkers, illicit substance users, alcoholics)
- 7- Plans to start or stop a medication that may affect appetite/weight-loss during the intervention period
- 8- Have started a medication within 6 months that is affecting appetite/weight-loss
- 9- Plans to move out of the area during the treatment period
- 10- Pregnancy/breastfeeding or plans of becoming pregnant during the study period
- 11- Is participating in another weight-loss program
- 12- Can not successfully record eating behavior in the MyFitnessPal app
- 13- A) Had bariatric surgery less than one year ago

B) If the potential participant had bariatric surgery over a year ago, their weight has not been stable for at least 6 months

1.8 Check all materials/methods that will be used in recruiting participants:

- Telephone script

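### Delay-discounting hypothesis 2 predicts no reduction in the HT arm, but the plan has only a difference test and no margin or interval rule, so a non-significant result could be misread as no change, chiefly in Cohort 2

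*Combined protocol and SAP*

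**What the plan says.** Section 1.22 lists three delay-discounting hypotheses under secondary analyses in each of Cohorts 1 and 2. The first predicts a reduction in the EFT arm. The second predicts none in the HT arm: "2- The HT group will not have a reduction in delay discounting over time (7, 10, 14, 18, 26) compared to baseline" for Cohort 1 and "2- The HT group will not have a reduction in delay discounting over time (11, 19, 20) compared to baseline" for Cohort 2. The third is the between-arm statement, for Cohort 2: "3- The EFT vs. the HT group will have a reduction in delay discounting over time (11, 19, 20").

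One analysis is named: "A two-way repeated measures ANOVA will be conducted to determine differences in delay discounting between the EFT and HT groups over time". No alpha level, equivalence margin, confidence-interval criterion or within-arm contrast is given for it. Section 1.23 says that no power analysis was done.

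HT is the CONTROL arm, as the Cohort 3 text of section 1.7 shows: "Unlike Cohort 1 and 2, there will be no CONTROL (HT) group". Section 1.3 gives 20 control dyads in Cohort 1 and 10 in Cohort 2 ("half of the families will receive EFT training (N=10) and the other half will receive a control thought training program (N=10").

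**The concern.** Hypothesis 2 asserts that something does not happen. A test of difference can reject no change or fail to reject it, but it cannot establish it. Without a margin, the only result that could be put forward as support is a non-significant HT change, and small arms produce that result easily.

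What is at stake is the mechanism claim. Section 1.5 gives reduced discounting as the reason EFT should work. If EFT is significant against its own baseline and HT is not, hypotheses 1 and 2 both appear confirmed and the fall looks specific to EFT. The same pattern can arise when both arms fall equally. An equal fall is conceivable, since both arms repeat the same task and share the programme apart from the cues. No figure in the documents says that it occurs.

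**Working it through.** The plan gives no power, effect size or SD, so there is no figure of its own to reproduce. What follows is an illustration.

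**Inputs from the documents.** HT arm n = 10 (Cohort 2) and n = 20 (Cohort 1), section 1.3. Later visits: sessions 11, 19, 20 (Cohort 2) and weeks 7, 10, 14, 18, 26 (Cohort 1), section 1.22.

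**Assumptions.** True HT fall of 0.5 baseline SD at every later visit; two-sided 5%; parents and children analysed separately; complete data; equal correlation r between all visits, taken as 0.5, 0.7 and 0.8.

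**Step 1, single visit against baseline.** SD of change = √(2(1−r)) baseline SD, which is 1.000, 0.775 and 0.632. Noncentrality = 0.5√n / SD of change. Power comes from the noncentral t with n−1 degrees of freedom (critical value 2.262 for n = 10, 2.093 for n = 20).

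| n | r | noncentrality | power | HT non-significant |
|---|---|---|---|---|
| 10 | 0.5 | 1.581 | 0.293 | 71% |
| 10 | 0.7 | 2.041 | 0.446 | 55% |
| 10 | 0.8 | 2.500 | 0.606 | 39% |
| 20 | 0.5 | 2.236 | 0.564 | 44% |
| 20 | 0.7 | 2.887 | 0.782 | 22% |
| 20 | 0.8 | 3.536 | 0.918 | 8% |

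**Step 2, within-arm time effect over all visits.** F noncentrality = n Σ(μⱼ − μ̄)² / (1−r). Cohort 2 has 4 visits, so Σ = 0.25 × 3/4 = 0.1875. At r = 0.5 the noncentrality is 10 × 0.1875 / 0.5 = 3.75 on 3 and 27 df. Cohort 1 has 6 visits, so Σ = 0.25 × 5/6 = 0.2083. At r = 0.5 the noncentrality is 20 × 0.2083 / 0.5 = 8.33 on 5 and 95 df. Non-significant at r = 0.5 / 0.7 / 0.8: Cohort 2, 70% / 53% / 34%; Cohort 1, 44% / 19% / 5%.

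**Step 3, stricter reading.** Hypothesis 2 covers every later visit, so a significant fall at any one of them could count against it. Simulation (100,000 trials per setting, visits unadjusted) gives the chance that no visit is significant: Cohort 2, 46% / 28% / 15%; Cohort 1, 11% / 3% / 0.3%.

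**Step 4, other sensitivities (single visit).**
- At r = 0.9 the non-significant rate is 12% (n = 10) and 0.3% (n = 20).
- Treating parents and children as independent people doubles n. Cohort 2 then takes the n = 20 rates of 44% / 22% / 8%, and Cohort 1 becomes 13% / 2% / 0%.
- Bonferroni adjustment over visits works the other way. At r = 0.5, per-visit power falls to 15% (n = 10, 3 visits) and 30% (n = 20, 5 visits).

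**Step 5, both arms fall by the same 0.5 SD.** The arms are independent, so the chance of EFT significant and HT not, at a single visit, is power × (1 − power). At r = 0.5 / 0.7 / 0.8:
- n = 10: 0.293 × 0.707 = 21%; 0.446 × 0.554 = 25%; 0.606 × 0.394 = 24%.
- n = 20: 0.564 × 0.436 = 25%; 0.782 × 0.218 = 17%; 0.918 × 0.082 = 8%.

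A direct two-sided 5% test between two equal arms favours EFT in 2.5% of trials.

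**Step 6, precision of the HT change.** The 95% half-width is critical t × SD of change / √n. For n = 10: 0.72 / 0.55 / 0.45 baseline SD. For n = 20: 0.47 / 0.36 / 0.30.

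**The case against.** The decision rule is an inference. Nothing in section 1.22 says that hypothesis 2 counts as supported when the HT change is not significant, and the ANOVA is described as comparing the arms. That stands: a reader should not take the rule as stated plan content. The gap remains, because no other criterion is given for a prediction framed against baseline.

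The valid comparison is already there. Hypothesis 3 sets EFT against HT and the ANOVA covers group by time. It would be wrong to infer that the plan has no sound test of the EFT effect on discounting. What it lacks is any statement that this comparison takes precedence over the paired within-arm predictions.

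A reader might also infer that a real CONTROL reduction would often be missed in both cohorts. The documents do not support that. The 0.5 SD fall is illustrative, section 1.5 attributes reduced discounting to EFT, and the Cohort 1 rates are small under several reasonable readings. Even in Cohort 2 the rate falls to 15% on the any-visit reading at correlation 0.8.

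Nor does low precision favour the EFT theory overall. Small arms make hypotheses 1 and 3 harder to support: at n = 10 and correlation 0.5, a 0.5 SD fall in EFT is detected at a single visit only 29% of the time.

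**Conclusion.** The point holds as a flaw of inference in a secondary analysis. Hypothesis 2 is a no-change prediction with no criterion that could establish it, and this does not depend on any assumed effect size.

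Its practical size does depend on assumptions. For a true HT fall of 0.5 baseline SD and correlations of 0.5 to 0.8, Cohort 2 would show a non-significant HT change in 39–71% of trials at a single visit, and in about 15–46% if any significant visit counts against the hypothesis. For Cohort 1 the ranges are 8–44% and about 0.3–11%. The problem is therefore substantial in Cohort 2 and assumption-dependent in Cohort 1.

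Under equal falls in both arms, the misleading pattern at a single visit arises in about 21–25% of Cohort 2 trials and 8–25% of Cohort 1 trials, against 2.5% for the direct comparison. The primary weight comparison is not touched by this point.

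**What to change.** In section 1.22, in the secondary analyses of both cohorts, replace delay-discounting hypothesis 2 with text to this effect:

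*The change in the HT group will be reported with a 95% confidence interval; a non-significant change will not be interpreted as absence of a reduction. The conclusion that EFT reduces delay discounting relative to HT rests on hypothesis 3 (the group-by-time comparison).*

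If a no-reduction claim is to be kept, allow it only when the 95% interval for the HT change excludes a reduction as large as a margin fixed in advance. With a margin of 0.5 baseline SD, for example, and an HT arm that truly does not change, Cohort 2 could make the claim at a single visit in 29% / 45% / 61% of trials at correlation 0.5 / 0.7 / 0.8. These equal the step 1 power figures by symmetry.

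The cost is two or three sentences, with no new data, visits or participants. The sponsor gives up the claim that CONTROL left discounting unchanged unless the interval supports it.
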